4.0 Statistical Considerations

4.1 Sample Size

The primary statistical endpoint of this study is to evaluate the safety and feasibility of vaccine boosting with lethally irradiated allogeneic pancreatic tumor cells transfected with the GM-CSF gene. Among patients who have previously been treated with the vaccine, the cohort is limited to those who continue to have no disease recurrence for at least 1 year after treatment. Currently, there are three potentially eligible patients from the original phase I study, and 14 from the phase II study. A total of up to 17 previously treated patients will be eligible to continue to receive vaccine treatment in the form of semi-annual boosts. The second cohort of vaccine naïve patients who have been recurrence free for at least 28 days following adjuvant therapy will be given three priming vaccines each a month apart, followed by semi-annual vaccine boosts in order to determine the feasibility of administering the vaccination to vaccine naïve patients and to obtain initial estimates of the efficacy of such treatment with respect to prolonging disease-free status. As of Amendment #9, participants will be switched to annual vaccinations. We will base our determination of feasibility by estimating the proportion of patients with a dose limiting toxicity (DLT) within 28 days of the first vaccine treatment. Between 20 and 45 vaccine naïve patients will be included. An initial group of 20 patients will be recruited and an interim analysis will be performed in order to guard against excessive toxicities relating to treatment. No DLTs have been observed in either the phase I or II studies. If there is significant evidence that more than 10% of the vaccine naïve patients have dose limiting toxicities within 28 days of the first vaccination, then the trial will be halted. If 6 out of 20 of the initial patients have DLTs, the lower bound of the exact 95% confidence interval for the proportion of patients with a DLT is 11.89%. Therefore, we will halt the trial due to excessive toxicity at the interim analysis if 6 or more patients have a DLT within the first 28 days of their first vaccine. Otherwise, an additional 20 vaccine naïve patients will be accrued. If 20 patients are accrued, the maximum width of the 95% confidence interval estimate of the proportion of patients with a DLT is 0.438. If the full cohort of 40 patients is accrued, then the maximum width of the 95% confidence interval is 0.309.

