The sample size was expanded to include a cohort of up to 45 vaccine-naïve research participants and 17 previously vaccinated research participants for a total sample up to 62 research participants.

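### Section 4.1 states maximum 95% CI widths for the DLT proportion by normal approximation (0.438 at n=20, 0.309 at n=40), though the plan's intervals are exact (0.456, 0.324), and it still treats 40, not 45, as the full vaccine-naïve cohort

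*Combined protocol and SAP*

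**What the plan says.** Section 4.1 judges feasibility by the proportion of patients with a DLT within 28 days of the first vaccination. It makes four statements that bear on this point.

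- **Halting bound.** The trial stops at the interim look on 20 vaccine-naïve patients if 6 or more have a DLT. The reason given is that at 6/20 "the lower bound of the exact 95% confidence interval for the proportion of patients with a DLT is 11.89" per cent, which is above the 10% threshold.
- **Precision.** "If 20 patients are accrued, the maximum width of the 95% confidence interval estimate of the proportion of patients with a DLT is 0.438". Then: "If the full cohort of 40 patients is accrued, then the maximum width of the 95% confidence interval is 0.309". Neither sentence names an interval method.
- **Accrual.** The paragraph opens with "Between 20 and 45 vaccine"-naïve patients. After a passed interim look it says "Otherwise, an additional 20 vaccine"-naïve patients will be accrued, which makes 40.
- **Expansion.** The closing sentence of 4.1 reads "The sample size was expanded to include a cohort of up to 45" vaccine-naïve participants "and 17 previously vaccinated research participants for a total sample up to 62 research participants".

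Section 4.2 specifies an exact 95% confidence interval for the DLT proportion, by cohort and by vaccination round.

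**The concern.** A maximum width is a promise: whatever count is observed, the reported interval will be no wider. That holds only if the width is computed for the interval that will be reported. Here the reported interval is exact, and an exact interval for a binomial proportion near one half is wider than the normal-approximation interval at these sample sizes. The two printed figures are the only interval widths that 4.1 gives for the DLT proportion, so a reader will take them as the precision of the primary safety estimate.

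Separately, the second figure is tied to a full cohort of 40, while the same section sets the maximum at 45. A reader cannot tell from 4.1 whether accrual after the interim look stops at 40 or 45, and no width is given for 45.

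**Working it through.** **Inputs.** From 4.1: two-sided 95% confidence; n = 20 and n = 40; stated widths 0.438 and 0.309; exact lower bound 11.89% at 6/20; maximum 45 vaccine-naïve and 17 previously vaccinated; total 62. From 4.2: exact 95% interval for the DLT proportion.

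**Step 1. Reproduce the stated widths.** The normal-approximation width is 2 × 1.96 × √(p(1 − p)/n), largest at p = 0.5.

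- n = 20: 2 × 1.96 × √(0.25/20) = 0.4383, printed as 0.438.
- n = 40: 2 × 1.96 × √(0.25/40) = 0.3099. This rounds to 0.310; the plan prints 0.309, so it was truncated.

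Other methods, taking the maximum width over all counts (n = 20 / n = 40), do not match:

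| Method | n = 20 | n = 40 |
|---|---|---|
| Wilson, Agresti-Coull | 0.401 | 0.296 |
| Jeffreys | 0.413 | 0.301 |
| Exact by test inversion | 0.436 | 0.314 |
| Normal with continuity correction | 0.488 | 0.335 |
| Clopper-Pearson | 0.456 | 0.324 |

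Only the plain normal approximation gives both printed figures.

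**Step 2. Confirm what exact means in this plan.** The Clopper-Pearson limits for x of n are the 2.5% quantile of Beta(x, n − x + 1) and the 97.5% quantile of Beta(x + 1, n − x). At 6/20 they are 0.1189 and 0.5428. The lower limit reproduces the 11.89%, so Clopper-Pearson is the working definition.

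**Step 3. Maximum exact widths.**

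| n | Count at maximum | Exact 95% interval | Exact maximum | Stated | Difference |
|---|---|---|---|---|---|
| 20 | 10 | 0.272 to 0.728 | 0.456 | 0.438 | 0.018 |
| 40 | 20 | 0.338 to 0.662 | 0.324 | 0.309 | 0.015 |
| 45 | 22 (or 23) | 0.337 to 0.642 | 0.305 | none | – |

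**Step 4. Where the stated maximum is exceeded.**

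- n = 20: 6/20 has exact width 0.424. 7/20 has 0.43828, which is 0.438 at the printed precision. 8/20 has 0.448, the first real excess. All such counts lie beyond the halting boundary of 6.
- Counts that let the trial continue (0 to 5 of 20): the widest is 5/20, at 0.404, inside the stated 0.438.
- n = 40: 13/40 has width 0.3056 and 14/40 has 0.3106, so the excess starts at 14. After a passed interim look (at most 5 DLTs), that needs at least 14 − 5 = 9 DLTs in the next 20 patients.
- n = 45: no count from 0 to 45 has an exact width above 0.309.

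**Step 5. Cohort sizes.** 20 + 20 = 40, and 40 + 17 = 57. The stated total of 62 is 45 + 17. The accrual step and the 40-patient width therefore do not fit the current maximum.

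**The case against.** The strongest reply has three parts.

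*The width sentences do not say exact.* As normal-approximation planning figures they are correct apart from one truncated digit, and the methods that drive decisions are already named. This stands in part: there is no computational slip, and nobody could doubt which interval governs halting or reporting. But a maximum width that the planned interval can exceed is not a maximum for that analysis.

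*The effect is close to nil.* The gap arises only at DLT rates far above anything expected; 4.1 records no DLTs in the phase I or II studies. This stands, and it limits the point to a correction of wording.

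*The expansion to 45 is disclosed.* The last sentence of 4.1 gives 45 and 62 outright. It does make the maximum clear. It does not revise the accrual step or the precision figure, which remain as current text.

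Two stronger readings are tempting and should not be drawn.

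- A reader might infer that the halting rule is in doubt, because a normal-approximation lower limit at 6/20 would be 9.92%, below the 10% threshold. The plan never uses that limit: the sentence that sets the rule specifies the exact bound, and 11.89% is right.
- A reader might see a contradiction between the lower end of 20 in 4.1 and the 30 to 45 in the synopsis and section 3.2. Twenty is the number included if the trial halts at the interim look, and section 3.2 presents 30 to 45 as an enrolment estimate. The two can both be true.

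**Conclusion.** The point holds as a minor inconsistency. The stated maximum widths are understated by 0.018 at 20 patients and 0.015 at 40, relative to the exact interval that the plan commits to. At 45 the printed 0.309 is slightly conservative against the exact maximum of 0.305. The 40-patient wording conflicts with the stated maximum of 45 and total of 62. The halting rule, the sample size and the analyses are unaffected.

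Two inferences support this. The normal approximation as the source of the widths is inferred from the match to both figures, since the plan does not name it. Exact is read as Clopper-Pearson because that method returns the plan's own 11.89%.

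**What to change.** In 4.1, name the method and restate the widths, for example: *If 20 vaccine-naïve patients are accrued, the maximum width of the exact (Clopper-Pearson) 95% confidence interval for the proportion with a DLT is 0.456; at the maximum of 45 it is 0.305.* Give 0.324 for 40 only if that size is kept as a planned stage.

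Reconcile the accrual step after the interim look, and the reference to 40 as the full cohort, with the maximum of 45 and the total of 62.

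The cost is wording only. The stated precision becomes slightly less favourable at 20 and 40. No halting rule, sample size or analysis changes.

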4.2 Analysis of Primary Endpoint: Safety and toxicity measurements

The primary endpoint of this study is safety as measured by local and systemic toxicity. These toxicities will be characterized according to the National Cancer Institute Common Terminology Criteria for Adverse Events, Version 3.0, and can be accessed and downloaded via the website: <http://ctep.cancer.gov/reporting>. Dermatologic toxicity measurements of the vaccine sites will be performed. For each patient cohort (vaccine naïve and vaccine treated), we will tabulate the number, type and degree of toxicities for each round of vaccination. In addition, we will estimate the proportion of individuals who have a DLT within the first 28 days of vaccination for each round with an exact 95% confidence interval.

4.3 Analysis of Secondary Endpoints

The analysis of the remaining endpoints are primarily descriptive in nature and are intended to be used to generate estimates of efficacy and hypotheses to be tested in later trials. For each endpoint, separate analyses will be performed for the vaccine naïve and vaccine treated patients.

4.3.1 Efficacy endpoints

The primary efficacy endpoint of interest is the overall survival (OS) of patients treated with vaccine boosts. The overall survival is defined as the time from the first vaccine boost until death. If a patient is lost to follow-up or the study is ended prior to death, the patient will be considered censored at their last recorded follow-up. For each cohort, Kaplan Meier curves will be constructed and the median survival estimates will be calculated with 95% confidence intervals using Greenwood's formula. Since the time between completion of treatment and the initiation of vaccine boosts will vary among subjects, we will use a Cox proportional hazards model to adjust for this delay in boosts.

We are also interested in investigating the effect of vaccine boosts on recurrence free survival (PFS). Patients who are treated at Johns Hopkins will be followed every 3 months and evaluated for recurrence. However, the standard of care follow-up varies from institution to institution. In order to prevent biasing our results, it is necessary to coarsen the follow-up interval so that every individual is evaluated at the same time points regardless of the institution. For example, if the only visits held in common among all patients were the semi-annual exams prior to vaccine boosting, it would be necessary to only consider the status of the JH patients at those two time points regardless of recurrence information gained from the additional 2 visits. This coarsening of the data may cause an overestimation of PFS. In order to take into account both potential forms of bias, we will perform our analysis of PFS on the entire cohort as well as the subpopulation of patients from Johns Hopkins (estimated to be approximately 50% of the research participants). PFS will be defined as the time from the first vaccine until evidence of disease recurrence. If a patient withdraws from the study prior to being diagnosed with progressive disease, they will be censored at the date of their last follow-up visit. If an individual dies prior to being diagnosed with progressive disease, they will be considered to have progressed at the date of their last follow-up visit. This is a conservative estimate if we count the disease recurrence at the next planned visit then this will bias the PFS time upward. The PFS will be summarized using Kaplan-Meier curves and estimates of median PFS with 95% confidence intervals based upon Greenwood's formula. Due to potential causes of bias discussed earlier, the results will be considered extremely preliminary. If the PFS estimates for patients treated at Johns Hopkins appear to be lower than that of the population as a whole and the Johns Hopkins patients are followed at more frequent intervals than the other patients, then this indicate that an overestimation of PFS may exist. No formal comparison is planned due to the small sample size. Such results could affect the future planning of follow-up treatment for patients in subsequent trials.

Measurements of immune response include but are not limited to mesothelin, prostate stem cell antigen (PSCA) and mutated k-ras-specific T cell responses. Continuous variables will be summarized with means and standard deviations. Dichotomous and categorical variables will be

summarized using proportions with exact 95% confidence intervals and counts, respectively. These summaries will be computed for each patient at two time points around each vaccine boost: pre-vaccination and four weeks post vaccination. Plot will be used to show the changes in immune response over time both for each individual and for each cohort. For each vaccine boost, comparisons in the pre and post-vaccine responses will be compared using paired t-tests (or Wilcoxon signed rank tests if appropriate) for continuous variables and Fisher's exact test for dichotomous or categorical variables. Associations between immune responses will be explored graphically (e.g. scatterplots, boxplots) and numerically (e.g. correlations, χ^2 tests).

Measurements of antitumor immunity include but are not limited to the measurement of shared tumor-specific antigens and k-ras specific antitumor immune responses. Autologous lymphocytes will be obtained from peripheral blood before each vaccination, and at four weeks following each vaccinations. The graphical and numerical analyses of these results will be the same as that described for measurements of immune responses and will be carried out for each cohort separately.

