1.0 Study Synopsis

Objectives:

Primary:

1. To evaluate the safety of primary and boost vaccinations with lethally irradiated allogeneic pancreatic tumor cells transfected with the GM-CSF gene vaccine in the treatment of patients with surgically resected adenocarcinoma of the head, neck, or uncinate of the pancreas

Secondary:

1. To estimate the association of specific *in vivo* parameters of immune response including, but not limited to mesothelin, prostate stem cell antigen (PSCA), and mutated *k-ras*-specific T cell responses, with clinical responses in patients who are receiving semi-annual vaccine boosting with lethally irradiated allogeneic pancreatic tumor cells transfected with the GM-CSF gene.
2. To estimate the efficacy of vaccine boosts in the treatment of patients with adenocarcinoma of the pancreas in terms of overall and recurrence free survival.
3. To use the serum GM-CSF levels as a measure of longevity of an allogeneic vaccine following a semi-annual boosting with lethally irradiated allogeneic pancreatic tumor cells transfected with the GM-CSF gene.
4. To determine the psychosocial and symptom profiles of patients with pancreatic cancer treated with an irradiated allogeneic GM-CSF secreting vaccine, and to explore changes over time. The psychosocial profile will include information about, but is not limited to demographics, quality of life, hope, trust, social support, decision control and advanced directives. The symptom profile will include but is not limited to pain, anorexia, fatigue, and mood state.

Study population:

In order to be considered for this study, patients need to meet following major criteria for inclusion: History of surgically resected pathologic stage 1 (no direct tumor extension beyond pancreas and no regional lymph node metastases), 2 (direct extension of tumor beyond pancreas), and/or 3 (regional lymph node metastases) adenocarcinoma of the head, neck, tail, or uncinate of the pancreas.

Have no radiographic evidence of pancreatic cancer disease recurrence.

Have not received any anti-cancer therapy in the past 28 days.

Study Design:

Eligible subjects will receive by intradermal administration the pancreatic tumor vaccine consisting of two irradiated, allogeneic pancreatic tumor cell lines transfected with the granulocyte macrophage-colony stimulating factor (GM-CSF) gene. There will be two cohorts of research participants: those who have previously received the pancreatic cancer vaccine (up to 17) and those

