3.4 Study Plan

3.4.1 Schedule

The previously vaccinated cohort receives the vaccine boost once every six months (+/- 30 days). As of Amendment #9, participants will be switched to annual vaccinations (+/- 30 days).

The vaccine naïve cohort receives the priming vaccine once every month (+/- 3 days) for three months, then a vaccine boost every six months (+/-30 days) beginning six months after prime vaccine #3. As of Amendment #9, participants will be switched to annual vaccinations (+/- 30 days).

At any time during the study additional leukapheresis or approximately 200 cc of blood may be obtained, and skin biopsies and photos may be taken of the vaccine sites and rashes, as clinical indicated, as long as the research participant is in agreement.

All research participants will be seen in the oncology outpatient center for vaccine administration and monitoring. Research participants will be monitored for at least 30 minutes following vaccination for evidence of acute reaction to the injected vaccine cells.

Research participants and the study team may request additional optional study visits for discussions and evaluations. During these patient-requested or clinically-indicated visits, additional assessments may be obtained, including, but not limited to a history and physical examination, toxicity assessment, vital signs, skin biopsy, photos, imaging tests, and clinical laboratory testing.

3.4.1.1.Both Cohorts- Vaccination #1:

This is the Prime Vaccination #1 for Vaccine Naïve Cohort and the Boost Vaccination #1 for Previously Vaccinated Cohort.

Baseline data and samples (May be obtained from Day-28 to Day 0)

1. A clinical evaluation to include vital signs, ECOG status, weight, review of systems, physical examination, and toxicity evaluation.
2. CT scans of the abdomen, pelvis, and chest. If the CT scan is not done at Hopkins, the research participant must provide the report and a copy of the scans. If the research participant is allergic to the CT scan contrast or the contrast is contraindicated (as in the case for renal insufficiency), a non-contrast CT of the chest and a MRI of the abdomen and pelvis will be obtained.

3. A leukapheresis for in vitro studies will be encouraged. If the research participant refuses a leukapheresis, approximately 200 cc of blood will be drawn.

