6. Photograph of vaccine sites (if clinically indicated)
7. 3 mm punch skin biopsy of representative vaccine site (if clinically indicated)

Day 4

1. Day 4 serum GM-CSF level

3.4.1.2. Vaccine Naive Cohort Only:

Prime Vaccination #2 Day 0 is the same as Day 28 (+/- 3 days) after Prime Vaccination #1

Day 0

1. A leukapheresis for in vitro studies will be encouraged. If the research participant refuses a leukapheresis, approximately 200 cc of blood will be drawn.
2. Vital signs before and after vaccine administration
3. Assessment for toxicities and vaccine site reactions from previous vaccinations, and medications.
4. Administration of vaccine (Topical lidocaine-based anesthetic may be placed about 1-2 hours prior to planned vaccine administration time to the intended vaccine sites.)
5. Photograph of vaccine sites (if clinically indicated)
6. Assessment for toxicities.
7. Monitor for 30 minutes after vaccine administration.
8. Several psychosocial and symptom instruments, including: quality of life, hope, and trust surveys. (See appendices for copies of the instruments).
9. If not previously enrolled on IRB # NA_00036444 (SKCCC J0248) entitled, Long term follow-up of patients who received lethally irradiated allogeneic pancreatic tumor cells transfected with the GM-CSF gene, the research participant will be encouraged to join the long-term follow-up study.
10. Collect and review the diary of prime vaccine #1. Provide new diary.

3.4.1.3. Vaccine Naive Cohort Only:

Prime Vaccination #3 Day 0 is the same as Day 28 (+/- 3 days) after Prime Vaccination #2

Day 0

1. A leukapheresis for in vitro studies will be encouraged. If the research participant refuses a leukapheresis, approximately 200 cc of blood will be drawn.
2. Vital signs before and after vaccine administration
3. Assessment for toxicities and vaccine site reactions from previous vaccinations, and medications.
4. Administration of vaccine (Topical lidocaine-based anesthetic may be placed about 1-2 hours prior to planned vaccine administration time to the intended vaccine sites.)
5. Photograph of vaccine sites (if clinically indicated)
6. Assessment for toxicities

7. Monitor for 30 minutes after vaccine administration
8. Several psychosocial and symptom instruments, including: quality of life, hope, and trust surveys. (See appendices for copies of the instruments).

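### In the vaccine-naive cohort, OS starts at the first boost and PFS at the first vaccine, so patients who fail before boosting count in PFS but have no OS time

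*Combined protocol and SAP*

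**What the plan says.** - **OS (4.3.1).** The section names OS in boosted patients as the primary efficacy endpoint of interest. Its origin is explicit: "The overall survival is defined as the time from the first vaccine boost until death". The result is reported by cohort: "For each cohort, Kaplan Meier curves will be constructed". A Cox model adjusts for the varying delay between the end of treatment and the start of boosting.
- **PFS (4.3.1).** "PFS will be defined as the time from the first vaccine until evidence of disease recurrence". On the population, "we will perform our analysis of PFS on the entire cohort", with a Johns Hopkins subset alongside. A death without diagnosed recurrence counts as progression at the last follow-up visit.
- **Aims.** Secondary objective 2 in the synopsis is "To estimate the efficacy of vaccine boosts in the treatment of patients with adenocarcinoma of the pancreas in terms of overall and recurrence free survival". For naive patients, section 4.1 also wants "to obtain initial estimates of the efficacy of such treatment with respect to prolonging disease-free status".
- **Schedule.** Section 3.4.1.1 makes vaccination #1 a prime for naive patients and a boost for previously vaccinated patients. For naive patients, "Prime Vaccination #2 Day 0 is the same as Day 28 (+/- 3 days) after Prime Vaccination #1", and prime #3 follows prime #2 by the same interval (3.4.1.3). Boosting is then described as "beginning six months after prime vaccine #3" (3.4.1).
- **Recurrence.** It is an exclusion criterion for boosting (3.2.5) and a reason to leave the study (3.4.6).

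**The concern.** Two endpoints that serve the same objective use different clocks and different patients in the naive cohort, and section 4.3.1 does not say so. The PFS curve starts at prime #1 and includes early failures. The OS curve starts months later, only in those still alive, recurrence-free and boosted. No section gives an OS origin to a naive patient who never reaches a boost, and none asks for the number of such patients.

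At stake is what the named primary efficacy endpoint means for the cohort that receives priming plus boosting. These estimates are intended to shape later trials (4.3). A reader who puts the two curves side by side, or subtracts median PFS from median OS, would be combining different populations.

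The previously vaccinated cohort is not affected if the first vaccine in the PFS definition means the first on this study, because that vaccination is boost #1. The definition does not say which is meant.

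**Working it through.** The plan gives no sample size, event count or expected median for OS or PFS, so there is no planned figure to reproduce. The finding rests on the text. The arithmetic below only shows its possible size.

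**Gap between the two origins (naive cohort).** Inputs: 28 days between primes (3.4.1.2, 3.4.1.3), six months from prime #3 to the boost (3.4.1), 30.44 days per month.

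(28 + 28)/30.44 + 6 = 1.84 + 6 = 7.84 months.

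With the visit windows (±3 days for each of two prime intervals, ±30 days for the boost), the shortest gap is (56 − 36)/30.44 + 6 = 6.66 months. The longest is (56 + 36)/30.44 + 6 = 9.02 months.

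**Share with a PFS event but no OS time.** Assume a Weibull time to recurrence with median *m* and shape *k*. The share failing before *t* = 7.84 months is 1 − 0.5^((*t*/*m*)^*k*). The documents give no median from first vaccine, so *m* = 9 to 24 months is an assumption. The maximum cohort is 45 (4.1).

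| Hazard | *m* = 24 | *m* = 12 | *m* = 9 |
|---|---|---|---|
| Constant (*k* = 1) | 20.3% (9 of 45) | 36.4% (16 of 45) | 45.3% (20 of 45) |
| Rising (*k* = 1.5) | 12.1% (5 of 45) | 30.7% (14 of 45) | 43.1% (19 of 45) |

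The OS curve would then rest on about 25 to 40 of 45 patients. Withdrawals and failures of other boost criteria would reduce this further.

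**Effect on median OS.** Assume Weibull time to recurrence, then exponential survival after recurrence with median 16 months (assumed), no deaths without recurrence, and a boost for everyone recurrence-free at 7.84 months. Compare median OS from first vaccine in all vaccinated patients with median OS from first boost in boosted patients (months):

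| Shape | *m* | All, from first vaccine | Boosted, from boost | Shift |
|---|---|---|---|---|
| 0.7 (falling) | 9 | 32.6 | 38.6 | +6.0 |
| 0.7 | 24 | 50.7 | 59.5 | +8.8 |
| 1 (constant) | 9 | 29.7 | 29.7 | 0 |
| 1 | 24 | 48.0 | 48.0 | 0 |
| 1.5 (rising) | 9 | 27.3 | 23.8 | −3.5 |
| 1.5 | 24 | 45.3 | 40.5 | −4.8 |

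Medians between 9 and 24 give shifts between these values. With one constant hazard, being recurrence-free at the boost carries no information about later risk, so the medians agree. They agree although a fifth to almost half of the patients are missing from the second.

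**Can the planned Cox adjustment repair this?** No. Its covariate is the delay to boosting, which exists only for boosted patients.

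**The case against.** The strongest defence is that each clock fits a stated aim. Objective 2 concerns boosts, and OS openly names boosted patients as its population. Section 4.1 wants disease-free status for naive patients, and PFS from first vaccine in the whole cohort provides that. No section asks for prime-plus-boost OS. Section 4.3 calls these analyses primarily descriptive, and 4.3.1 calls the PFS results extremely preliminary. All of this stands. It is why boost-origin OS should be kept and why nothing here touches the primary safety endpoint or the DLT rule. It does not make the two curves comparable, and it leaves the named primary efficacy endpoint without an estimate for the naive cohort as treated.

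A second defence is that the first vaccine in the PFS definition is shorthand for the first boost, since the paragraph opens with the effect of boosts. That is strained: the OS definition just before it uses the explicit term. The phrase about the entire cohort is set against the Johns Hopkins subset, but it is not limited to boosted patients.

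A reader might infer three stronger things that the documents do not support.

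- **That boost-origin OS is inflated.** The sign depends on the shape of the hazard, which is not given.
- **That the gap is really 13.8 months.** The boost criterion in 3.2.4 requires 12 months since the last vaccine, which would give 1.84 + 12 = 13.84. But 3.4.1 puts the first naive boost six months after prime #3, and the Amendment #9 sentence does not say whether that boost moves. This is one reading of a conflict, not an established figure.
- **That the historical comparison in 5.1 flatters the vaccine by a known amount.** That section matches on stage, surgery and adjuvant therapy. It states neither a recurrence-free requirement nor a control clock, so no size can be attached.

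**Conclusion.** The concern holds as a mismatch of population and time origin, confined to the naive cohort. The text establishes a gap of about 7.8 months and that patients failing within it have no OS time. The share affected, about 20%-45% (constant hazard) or 12%-43% (Weibull shape 1.5), rests on assumed recurrence medians of 24 to 9 months. The shift in median OS is zero under one constant hazard. It runs from about −4.8 to +8.8 months over those medians and shapes 0.7 to 1.5, with an assumed post-recurrence median of 16 months. No direction of bias can be claimed. Boost-origin OS is valid as a conditional estimate. The defect is that it is not labelled as one and has no unselected counterpart. It should be fixed, but no decision in the trial depends on it.

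**What to change.** **In 4.3.1:**
- For the naive cohort, add OS from the first vaccination on this study in all vaccinated patients, reported beside PFS from the same origin.
- Write *first vaccination on this study* in the PFS definition, for both cohorts.
- Keep OS from first boost for objective 2, labelled as conditional on being alive, recurrence-free and boosted.
- Report how many naive patients were never boosted, and why.

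**In 3.2.4 and 3.4.1:** reconcile the 12-month criterion with the six months after prime #3 for the first naive boost, because that interval sets the OS clock.

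**In 5.1:** for any historical comparison, use controls who are recurrence-free at the same time since resection as the trial patient at first vaccination, and start both clocks there.

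**Cost:** some wording, one extra analysis and a count. Survival figures may move either way. Deaths after patients leave the study are captured through long-term follow-up that needs separate consent (3.4.4), so its completeness should be reported. Boost-origin OS already has that dependence.
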